18.2. Subject's Consent

The investigator should explain the nature, scope, and expected results of the study to the participants of the clinical study in advance using their native language (mother tongue) so that they can easily understand. The investigator should ensure that the subject is free to decide their participation in the study and that he/she has a clear understanding that he/she can refuse to participate in the study without any damage or loss of profits or that he/she can stop at any time during the study.

The subject shall have time to fully consider the participation in the study after hearing the explanation about the study and can fully discuss with the family or acquaintances. The subject shall also be able to request explanations from the investigator at any time and receive satisfactory answers if he/she does not understand any part of the study.

The investigator shall obtain the consent from the subject in writing, and the informed consent form will be signed and dated by the investigator and the subject by hand. The original copy of the signed informed consent form must be kept by the investigator, and a copy must be given to the subject.

By signing the informed consent form, the subject agrees to participating in the clinical study, and the collection and use of the subject's personal information in connection with the clinical study. The personal information of the subject is used to identify the subject and to connect the clinical information collected during the clinical study process. The collected personal information is coded so that the individual's identity cannot be known and cannot used directly as clinical study data.

The scope of personal information collected in relation to the clinical study includes personal identification information (name, contact information, etc.), demographics, medical records (past medical history, treatment history, etc.), and results of tests performed in relation to the clinical study. All collected data should be treated in accordance with the laws, rules and regulations on the

Confidential Page 41 of 51

protection of personal privacy.

The investigator should not carry out any tests for the clinical study before obtaining a consent from the subject.

18.3. Institutional Review Board (IRB)

Before commencing clinical study, the investigator should be reviewed by the IRB for the investigator's brochure, clinical study protocol, informed consent form for subjects, method of recruiting subjects (including advertisements, etc.), and other information provided in writing to the subject. The IRB will send the results of the review for conducting the study to the sponsor and the investigator in writing prior to the commencement of the clinical study.

The principal investigator should conduct a clinical study after obtaining the IRB's approval of the clinical study protocol and any revisions or changes. In addition, events that may affect the safety of the patient including SAEs or the continued performance of clinical study, especially safety-related changes, must be reported to the IRB. A report on the progress should be submitted to the IRB once a year, and when the clinical study is completed, it should be notified to the IRB.

18.4. Monitoring and Inspection of Compliance with the Protocol

To ensure that the rights and welfare of the subjects are protected, verify the accuracy, completeness and verifiability of the data, and check that the clinical study is conducted according to the protocol and KGCP approved by the Minister of Ministry of Food and Drug Safety and IRB, monitoring planned by the sponsor will be performed.

A monitoring agent from the sponsor side will visit the study site conducting the study to check completeness and clarity of a case record form, compare with the base data, and conduct verification, etc. of the managerial task. And, the investigators should cooperated with this. During the monitoring visit, the monitoring personnel will review the informed consent form for subjects, patient recruitment and follow-up monitoring, recording and reporting of serious adverse events, distribution of investigational products, patients' compliance with the use and dose of investigational products, amount of investigational products, concomitant treatment, quality of data, etc. with the investigators.

The sponsor may conduct an audit as part of a credibility assurance and verify that the clinical study has been carried out in accordance with the protocol, SOP and relevant regulations. In addition, the Minister of Ministry of Food and Drug Safety can check whether the study was conducted according to the GCP and related regulations through the inspection. If reading study-related documents for monitoring or inspection is requested by the sponsor or officials of MFDS, the principal investigator or the head of study site should cooperate with this actively.

18.5. Confidentiality

All records that identify the subject should remain confidential. All documents related to clinical study such as case record forms should be recorded and identified with the subject identification code (subject number, initial), not the name of the subject. If there is a subject's name on documents provided to the sponsor (pathological report, medical imaging record, etc.) among medical records, it should be deleted before being provided to the sponsor.

The sponsor (monitoring personnel, etc.), IRB, and MFDS can read medical records of the subjects for the purpose of identifying the information collected, and the information exposed when they are read will be handled with utter confidentiality. And, the investigator will notify the subject of this.

Confidential Page 42 of 51

Protocol No. DW_UDCA005 Ver 2.3_23/Feb/2016 English Translation Version

18.6. Archiving Data

The investigator will take measures to prevent accidental or premature destruction of all documents related to the clinical study. It is recommended that the clinical study-related documents are retained for at least three years from the date of termination of the study after the completion or discontinuation of this study or the date of product license. The investigator should notify the sponsor in advance of the destruction of documents required for the study after the completion or discontinuation of the study. If the investigator can no longer keep the documents, he/she should inform the sponsor so that the related documents can be sent to the mutually agreed representative.

Appendix 1. ECOG Performance Status Scale*

Grade	Status
0	Fully active, able to carry on all pre-disease performance without restriction
1	Restricted in physically strenuous activity but ambulatory and able to carry out work of a light or sedentary nature, e.g., light house work, office work
2	Ambulatory and capable of all self-care but unable to carry out any work activities. Up and about more than 50% of waking hours
3	Capable of only limited self-care, confined to bed or chair more than 50% of waking hours
4	Completely disabled. Cannot carry on any self-care. Totally confined to bed or chair
5	Dead

Confidential Page **46 of 51**

^{*} As published in Am. J. Clin. Oncol.:

Protocol No. DW_UDCA005 Ver 2.3_23/Feb/2016

English Translation Version

Appendix 2. Questionnaire for Evaluation of Symptoms of Biliary Reflux

The following questions list five (or six) answers about how often the following gastrointestinal symptoms occurred over the past two weeks, how severe the symptoms were, and how much you suffered. Please mark those that apply with o in a number.

	How 0 = N			t occ	ur?	How			e v	ere	the	How	ba	_	were	the
	1 = 1					symptoms? 0 = None.			symptoms? 0 = None.							
	2 = 5		•			1 = V	ery	wea	k.			1 = Ve	ery w	eak.		
	3 = 9	to 12	2 days	3		2 = V	/eak	۲.				2 = Weak.				
	4 =	Eve	ry da	ау, а	lmost	3 = S	ome	ewha	at se	ver	e.	3 = Severe.				
	every	/ day				4 = S	eve	re.				4 = Ve	ery s	evere	·.	
						5 = V	ery	seve	ere.							
Pain in the upper abdomen (If it hurts or feels stiff.)	0	1	2	3	4	0	1	2	3	4	5	0	1	2	3	4
Heartburn (Stinging or burning sensation)	0	1	2	3	4	0	1	2	3	4	5	0	1	2	3	4
3. (Nausea, discomfort)	0	1	2	3	4	0	1	2	3	4	5	0	1	2	3	4

Confidential Page 47 of 51

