8.1. Inclusion Criteria

- 1) Patients who voluntarily agree to participate in the study and sign the informed consent form
- 2) Patients at least 19 years of age at the time of informed consent
- 3) Patients who were diagnosed with gastric cancer and underwent any one of the following gastrectomies
 - Total gastrectomy
 - Distal gastrectomy
 - Proximal gastrectomy
- 4) Patients who underwent D1+ or D2 lymph node dissection
- 5) Patients with ECOG performance status scale ≤ 1 point (Appendix 1)
- 6) Life expectancy of at least 3 months
- 7) Patients who can be enrolled in the study within 2 weeks from gastrectomy

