10.1. Study Design

This is a multicenter, randomized, double-blinded, placebo-controlled, phase 3 study. Subjects are patients who have been diagnosed with gastric cancer and underwent gastrectomy for treatment. Screening will be conducted on subjects who gave an informed consent to participate in the study. Subjects who meet the inclusion criteria and do not qualify as exclusion criteria will be randomly assigned to DWJ1319 300 mg (DWJ1319 300 mg, once a day), DWJ1319 600 mg (DWJ1319 300 mg, twice a day), or placebo (1: 1: 1). For randomization, stratified randomization using the study site, the lymph node resection range (D1+, D2), and the type of gastrectomy as the stratification factors will be performed and randomization will be performed within 2 weeks from gastrectomy. During the study period, the subjects will visit the study site at screening, randomization (Day 1) and at 3-month interval after the administration of investigational product (at 3, 6, 9, and 12 months) to undergo protocol-specified tests and procedures at each visit. However, any subject with formation of gallstone confirmed during the treatment period will terminate the study at the time of confirmation.

Visit 1	Visit 2	Visit 3	Visit 4	Visit 5	Visit 6
Until Week -2	Day 1	Month 3 ± 1 Week	Month 6 ± 1 Week	Month 9 ± 1 Week	Month 12 ± 1 Week
Screening	Randomizatio n	Treatment period			

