11.2.9. Assessment of Biliary Reflux Symptoms and Upper Gastrointestinal Endoscopy

The assessment of symptoms for a biliary reflux will be conducted at Visits 2 (baseline), 3, 4, 5 and 6, or at the time of early termination/withdrawal to determine the gallstone formation. The subjects completes a questionnaire (Appendix 2) in three areas including the frequency, strength, and the level of pain of the representative symptoms of biliary reflux (upper abdominal pain, heartburn, and nausea).

In addition, the investigator will perform an upper gastrointestinal endoscopy at Visits 3 and 6 to confirm the actual reflux of bile and record the results. There is no need for a separate endoscopy, but endoscopy results under routine clinical practices can be collected and used.

To diagnose bile reflux during the upper gastrointestinal endoscopy, the investigator will evaluate the status of bile reflux (Y/N) by observing the remnant stomach or the anastomotic area and determine it as bile if a yellow liquid is observed in the assessed area. If bile reflux is observed, gastritis is assessed as well according to the following criteria: ^{29),30)}

- 1) Grade 0: No flare on mucous membrane or the remnant stomach or anastomotic area.
- Grade 1: Mild redness is observed in the mucous membrane of the remnant stomach or anastomotic area.
- 3) Grade 2: A comb-shaped redness is observed on mucous membrane of the remnant stomach or anastomotic area.
- 4) Grade 3: Severe redness and edema are observed on mucous membrane of the remnant stomach or throughout the anastomotic area.

[figure not shown]

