11.3.2. Visit 2 (randomization and administration of investigational products, Day 1)

Visit 2 will take place within two weeks after the screening (Visit 1). If the subject is suitable for participating in the clinical study, the following procedures will be performed:

- Vital signs (blood pressure, pulse) are measured.
- Changes in the medication history and therapeutic potential are checked compared to previous visits.
- Changes in the medical history/prior surgery are checked compared to previous visits.
- The inclusion/exclusion criteria are re-verified.
- Randomization is performed.
- Investigational products are prescribed, and guidance is provided for taking medications.
- A questionnaire to evaluate the symptoms of biliary reflux is prepared.
- The subsequent visit dates are determined.

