14.4.3. Other Efficacy Endpoints

1) Changes in the bile reflux symptoms from baseline value (score for each area and the overall score) at 3, 6, 9, and 12 months

For scores of questionnaire on bile reflux symptoms, the score of each typical symptom (upper abdominal pain, heartburn, nausea) and the total score of symptoms will be presented in three categories which are frequency, intensity, and the level of distress.

Descriptive statistics (mean, standard deviation, minimum, median, and maximum) for changes in the bile reflux symptom score and changes compared to the baseline value at each time point are provided for each treatment group. And the difference in the changes in the bile reflux symptom score between each treatment group of DWJ1319 and the placebo is analyzed using the analysis of covariance with the lymph node resection range and the type of gastrectomy as covariates.

 Percentage of subjects who developed biliary reflux according to the upper gastrointestinal endoscopy at 3 and 12 months

The frequency and proportion of subjects with biliary reflux at each time point and the corresponding 95% confidence interval are provided for each treatment group. And the difference in the biliary reflux onset rate between each treatment group of DWJ1319 and the placebo is analyzed using a logistic regression model with the lymph node resection range and the type of gastrectomy as covariates.

Percentage of subjects with significant AST and ALT abnormalities at 6 and 12 months
 The frequency and percentage of subjects for whom the AST and ALT of the laboratory test were

Confidential Page 35 of 51

determined to be clinically significant abnormalities at the 6th and 12th month after gastrectomy were presented, and the difference between each dose of DWJ1319 versus placebo for the clinically significant abnormal percentage are analyzed using a logistic regression model with the lymph node resection range and type of gastrectomy as covariates.

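### The reflux questionnaire's two-week recall, used at a baseline within two weeks of gastrectomy, mixes pre-operative days with acute recovery, so within-arm change cannot be read as change in bile reflux

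*Protocol*

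**What the plan says.** Appendix 2 of the protocol asks "how often the following gastrointestinal symptoms occurred over the past two weeks", how severe the symptoms were and how much they troubled the subject. The three symptoms are upper abdominal pain, heartburn and nausea. The frequency answers are counted in days within the fortnight; the other two sets of answers are severity ratings.

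Section 11.2.9 has the assessment "conducted at Visits 2 (baseline), 3, 4, 5 and 6", and section 11.3.2 lists the questionnaire among the Visit 2 (Day 1) procedures, alongside randomization. Section 10.1 states that "randomization will be performed within 2 weeks from gastrectomy", and inclusion criterion 7 in section 8.1 admits "Patients who can be enrolled in the study within 2 weeks from gastrectomy".

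Section 14.4.3, item 1, defines the endpoint as "Changes in the bile reflux symptoms from baseline value (score for each area and the overall score) at 3, 6, 9, and 12 months". It asks for descriptive statistics by arm and says that the difference between each DWJ1319 arm and placebo "is analyzed using the analysis of covariance with the lymph node resection range and the type of gastrectomy as covariates". The baseline score is not among the covariates. Sections 6.1.3 and 8.4.3 of the statistical analysis plan keep the same change score and the same two covariates.

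Nothing shortens the recall at Visit 2, limits it to post-operative days, or sets a minimum time since surgery.

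**The concern.** A change from baseline is informative about a symptom only if the baseline measures that symptom in a state comparable with follow-up. Here a 14-day look-back is applied at a visit no more than 14 days after the operation. The look-back therefore covers days before gastrectomy, when post-gastrectomy reflux could not occur, together with the first days after it, when abdominal pain and nausea may come from the operation itself. The follow-up scores, from Month 3 on, cover neither.

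Two things are at stake. The by-arm tables of change will contain the effect of surgery and recovery from it, and could be taken for change in reflux. And the treatment comparison subtracts a baseline that may have little to do with the later score, which adds noise.

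**Working it through.** The documents give no numerical target for this endpoint, so there is no planned figure to reproduce. The sample size of 138 per group concerns the primary endpoint and does not bear on the point.

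**Inputs from the protocol**
- Recall window: 14 days (Appendix 2).
- Baseline visit: Visit 2, Day 1, at randomization (sections 11.2.9 and 11.3.2).
- Latest time of Visit 2: 14 days after gastrectomy (sections 8.1 and 10.1).
- Outcome: change from baseline; covariates lymph node range and gastrectomy type only (section 14.4.3).

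**Step 1: what the baseline window covers.** For Visit 2 on post-operative day k (k at most 14), the pre-operative days in the window number 14 − k, a share of (14 − k)/14.

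| k | Pre-operative days | Share of window |
|---|---|---|
| 3 | 11 | 79% |
| 5 | 9 | 64% |
| 7 | 7 | 50% |
| 10 | 4 | 29% |
| 14 | 0 | 0% |

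The documents give no distribution of k. If k were uniform on 1 to 14 (an assumption), the mean share would be 91/(14 × 14) = 46%. At k = 14 no pre-operative day is left, but the whole window is then the first fortnight after surgery.

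**Step 2: can the parts be separated afterwards?** Not from the questionnaire, which gives one answer per item for the whole window. Section 10.3 also says that painkillers and drugs for gastrointestinal symptoms given in hospital before enrolment need not be recorded, unless continued after discharge. Treatment that may have altered the baseline symptoms can therefore go unrecorded.

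**Step 3: precision.** Assume equal variances at Visit 2 and at follow-up, and a correlation ρ between the two scores. Standard errors of the treatment difference, relative to analysing the visit score without baseline, are:
- change score, not adjusted for baseline (as planned): √(2(1 − ρ));
- visit score with baseline as a covariate: √(1 − ρ²).

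| Assumed ρ | Change score | Visit score, baseline as covariate |
|---|---|---|
| 0 | 1.41 | 1.00 |
| 0.2 | 1.26 | 0.98 |
| 0.4 | 1.10 | 0.92 |
| 0.5 | 1.00 | 0.87 |
| 0.7 | 0.77 | 0.71 |

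The ratio of the second variance to the first is (1 − ρ²)/(2(1 − ρ)) = (1 + ρ)/2, which never exceeds 1. Under these assumptions the covariate analysis is never less precise than the planned one, whatever ρ is.

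**The case against.** The strongest objection is that the planned inference is between arms. The baseline is taken at randomization in a double-blind trial, so its peri-operative content is the same in expectation in all three arms and cancels in the contrast. This stands. A reader might infer that the treatment comparison is biased, or that the endpoint tells nothing about reflux; the documents support neither.

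A reader might also infer that within-arm change will mostly show recovery from surgery. That is not established. Pre-operative days may dilute the acute symptoms, and the documents contain no symptom data, so even the direction of the net effect is unknown. What is supported is that the change cannot be attributed to reflux.

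Further objections stand in part:
- **The problem is partly inherent.** Prophylaxis starts within two weeks of surgery, so any pre-dose score is peri-operative. The long recall adds to this but is not its only cause. That limits what a new form could achieve; it does not make the change interpretable.
- **The day shares apply directly only to the frequency answers.** Intensity and distress are severity ratings, so the percentages do not carry over to them. Those ratings still refer to the same mixed window.
- **The loss of precision is conditional.** It vanishes at ρ = 0.5 and reverses above, and it would be removed by adjusting for baseline. This is correct, and the fix uses it. Adjustment does not, however, repair the reading of the within-arm tables.
- **By-arm change is only described, not tested.** True for section 14.4.3, so the harm is a risk of misreading rather than a false claim in the plan.

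**Conclusion.** The point holds as a minor one. From the protocol's own dates, every permitted baseline window reaches back to the day of gastrectomy or earlier, in a mixture of pre-operative and early recovery days that varies with the day of Visit 2. Within-arm "Changes in the bile reflux symptoms from baseline value" cannot be read as change in bile reflux. This part needs no assumption beyond the visit timing and the recall period.

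The precision part does rest on assumptions: equal variances and a weak correlation, neither of which the documents give. The planned analysis has a standard error 26% larger than the visit score at ρ = 0.2 and 10% larger at 0.4, no penalty at 0.5, and a gain above that.

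The endpoint is listed under other (exploratory) endpoints. The primary analysis, the fixed-sequence test, the sample size and the secondary endpoints are untouched.

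**What to change.** In section 14.4.3(1), make the symptom score at Months 3, 6, 9 and 12 the analysed variable and add the Visit 2 score as a covariate next to lymph node range and gastrectomy type. Carry the same wording into the synopsis and section 8.4.3 of the statistical analysis plan. Report the Visit 2 scores descriptively under the label *peri-operative*, and state that within-arm change from Visit 2 is not interpreted as change in bile reflux.

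Leave the form unchanged. It is tempting to ask at Visit 2 only about the time since the operation, but this would give subjects unequal recall lengths on a day-count scale: someone at day 5 could not reach the 9-to-12-day category. The baseline would no longer share a scale with follow-up, and a change during enrolment would split it into two instruments.

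The cost is the wording of one exploratory analysis and one model term. No new data are needed, and no further subjects are lost, because the change score already requires a Visit 2 value.

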Appendix 3. Expected Side Effects and Precautions for Use

Expected side effects of DWJ1319 and precautions for use are based on the approval of Ursa-D Capsule 300 mg.

- 1. It should not be given to the following patients:
- 1) Patients with hypersensitivity to this component or bile acid
- 2) Patients with severe biliary obstruction (may worsen the symptoms because of the choleretic action)
- 3) Patients with fulminant hepatitis (may worsen the symptoms)
- 4) Patients with calcified cholesterol gallstones or patients with radiation-impermeable gallstones or bile pigment gallstone
- 5) Patient with non-functional gallbladder
- 6) Patients requiring cholecystectomy due to continuous acute cholecystitis, cholangitis, biliary obstruction, gallstone pancreatitis, and biliary gastrointestinal tract fissura
- 7) Women who are pregnant or who may be pregnant and breast feeding women
- 8) Children
- 9) Patients with a kidney disease
- 10) Patients with peptic ulcer (acute gastric or duodenal ulcer) (may worsen the symptoms due to mucous membrane irritation)
- 11) Patients with colitis and enteritis such as Crohn's disease
- 2. Caution will be taken when giving it to the following patients:
- 1) Patients with severe pancreatic disease (can worsen the original disease)
- 2) Patients with gallstones in the bile ducts (may cause cholestasis because of the choleretic action.)
- 3) Patients with varicose vein bleeding, hepatic coma, ascites, and who suddenly require a liver transplantation

3. Adverse events

The nature and frequency of adverse events were similar in all groups.

The table below is a comprehensive table of adverse events reported with an incidence of 5% or more.

	Diss	olution of gallstone		
		ycholic acid /day (n = 155)		acebo = 159)
Whole body	N	(%)	N	(%)
Allergy	8	(5.2)	7	(4.4)
Chest pain	5	(3.2)	10	(6.3)
Fatigue	7	(4.5)	8	(5.0)
Virus infection	30	(19.4)	41	(25.8)
Digestive system				
Abdominal pain	67	(43.2)	70	(44.0)
Cholecystitis	8	(5.2)	7	(4.4)
Constipation	15	(9.7)	14	(8.8)
Diarrhea	42	(27.1)	34	(21.4)
Indigestion	26	(16.8)	18	(11.3)
Flatulence	12	(7.7)	12	(7.5)

Confidential Page 48 of 51

Gastrointestinal disturbance	6	(3.9)	8	(5.0)
Nausea	22	(14.2)	27	(17.0)
Vomiting	15	(9.7)	11	(6.9)
Musculoskeletal				
system Arthralgia	12	(7.7)	24	(15.1)
Arthritis	9	(5.8)	4	(2.5)
Back pain	11	(7.1)	18	(11.3)
Myalgia	9	(5.8)	9	(5.7)
Nervous system				
Headache	28	(18.1)	34	(21.4)
Insomnia	3	(1.9)	8	(5.0)
Respiratory system				
Bronchitis	10	(6.5)	6	(3.8)
Cough	11	(7.1)	7	(4.4)
Pharyngitis	13	(8.4)	5	(3.1)
Rhinitis	8	(5.2)	11	(6.9)
Nasosinusitis	17	(11.0)	18	(11.3)
Upper respiratory tract infection	24	(15.5)	21	(13.2)
Genitourinary system Urethral infection	10	(6.5)	7	(4.4)

	Ga	llstone prevention		
		olic acid 600 mg = 322)		cebo : 325)
	N	(%)	N	(%)
Whole body				
Fatigue	25	(7.8)	33	(10.2)
Virus infection	29	(9.0)	29	(8.9)
Influenza-like symptoms	21	(6.5)	19	(5.8)
Digestive system				
Abdominal pain	20	(6.2)	39	(12.0)
Constipation	85	(26.4)	72	(22.2)
Diarrhea	81	(25.2)	68	(20.9)
Flatulence	15	(4.7)	24	(7.4)
Nausea	56	(17.4)	43	(13.2)
Vomiting	44	(13.7)	44	(13.5)
Musculoskeletal				
system Back pain	38	(11.8)	21	(6.5)
Musculoskeletal pain	19	(5.9)	15	(4.6)

Confidential Page **49 of 51**

Nervous system				
Dizziness	53	(16.5)	42	(12.9)
Headache	80	(24.8)	78	(24.0)
Respiratory system				
Pharyngitis	10	(3.1)	19	(5.8)
Nasosinusitis	17	(5.3)	18	(5.5)
Upper respiratory tract infection	40	(12.4)	35	(10.8)
Skin and other organs Hair loss Genitourinary system	17	(5.3)	8	(2.5)
Menstrual pain	18	(5.6)	19	(5.8)

In addition to the above table, the following adverse events may occur:

- 1) Interstitial pneumonia: If interstitial pneumonia is accompanied by fever, cough, dyspnea, or an abnormal chest X-ray appears, discontinue administration and take appropriate actions.
- 2) Others: In rare cases, systemic malaise, dizziness, calcification of gallstones, elevated liver enzymes (ALT, ALP, AST, γ-GT) and leucopenia may occur.
- 3) If there is a rise in serum bilirubin, administration should be stopped, and proper measures should be taken.

4. General cautions

- 1) When given to patients with high jaundice in the liver cirrhosis, symptoms may worsen, so it should be administered carefully.
- 2) Hepatic enzyme values of the plasma (ALT, ALP, AST, γ-GT, total bilirubin) should be examined regularly during the treatment.
- 3) Severe adverse events due to overdose are unlikely to occur, but liver function tests should be performed if necessary.

5. Interaction

- 1) There is a risk of increasing the action of the following drugs: Oral diabetic agent (tolbutamide)
- 2) The following drugs may interfere with the absorption of this drug and reduce the effect of the drug.
 - : Antacids containing cholestyramine, colestipol, medicinal charcoal, magnesium and aluminum hydroxide
- 3) Drugs that increase cholesterol secretion in the liver (e.g., oral contraceptives containing estrogen and lipid-lowering drugs such as clofibrate) may weaken the action of this drug because they promote cholesterol gallstone formation.
- 4) Concomitant use with drugs that damage the liver should be avoided.

6. Administration to pregnant women and breast feeding women, children and the elderly

Pregnant women

Studies on reproductive toxicity were performed in rats and rabbits up to 200 times the treatment dose of this drug, and no evidence of damage to the fetus or reproductive capacity was found in rats at 20-100 times the dose of the human dose. In rabbits, such evidence was not found at five times the human dose. Studies in which rats were given 100-200 times the human dose showed some reductions in fertility and the number of embryos born in the same womb. No adequate and well-controlled clinical study has been performed in pregnant women. However, during the clinical study period of this drug, there was no effects on the fetuses or newborns of 4 women who were unintentionally treated with a treatment dose during the first 3

Confidential Page 50 of 51

Protocol No. DW_UDCA005 Ver 2.3_23/Feb/2016

English Translation Version

months of pregnancy. This drug is not considered to cause damage to the fetus, but it is not recommended to take this drug during pregnancy, as such possibility cannot be excluded.

2) Breast feeding women

It is not known whether this drug is excreted through human milk. Because many medications are excreted through human milk, it is not recommended to give this drug to breast feeding women.

3) Children

The safety and efficacy of this drug in pediatric patients has not been established.

4) Elderly

